1.03 CRU: Nursing Resources

3.01

CRU Nursing Visits:

Please Add Each Visit

	Title	Visit #	Visit Length	Admissions	Comments
View	Targeted breast milk fortification	1	60 Minutes	no	CRU will obtain PEAPOD prior to discharge

View: CRU 01-06 Human Performance Lab Tests and Measurements

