This will be a prospective randomized control study of preterm infants less than 1500 grams [very low birth weight (VLBW)] receiving human milk (maternal or donor) will be included. The control group will receive adjustment of total parenteral nutrition (TPN) per NICU guidelines as enteral feedings are advanced followed by standard fortification of human milk. The intervention group will have TPN (protein and lipids) adjusted based on analysis of human milk as feedings are advanced to provide goal 4g/kg/day of protein and 100-130 kcal/kg/day followed by targeted fortification of breast milk based on human milk analysis to continue to provide 4 g/kg/day of protein and 100-130 kcal/kg/day for once full feeds are achieved. The primary aim of this study is to evaluate the growth, anthropometric measurements, and body composition, to see if targeted fortification improves neonatal growth. By optimizing neonatal growth and nutrition there is potential to also have an impact on other morbidities and long term neurodevelopmental outcomes.

This is your abstract also known as a synopsis from an industry sponsored study. Please limit to 500 words.

7.2 * **What are the specific aims of this study i.e. what are the question(s) this research intends to answer? Provide at a maximum 3 primary and 3 secondary aims.**

The aim of this study is to demonstrate improved growth and body composition in VLBW infants by using human milk analysis as a tool to guide when adjusting TPN and lipids followed by targeted fortification of breast milk at full feeds to provide 4g/kg/day of protein 100-130 kcal/kg/day, compared to those who receive standard management of TPN per guidelines and standard fortification.

The primary outcome measured will be body composition measurement 4 weeks after achieving full feeds with targeted fortification, or at NICU discharge, whichever comes first.

Secondary outcome variables:

1) Weight gain velocity

2) Anthropometric measurements including weight, length, head circumference, and mid upper arm circumference or skinfold thickness

This is your Hypothesis also know as your aims (NIH) or safety and efficacy aims (industry). Please list no more than 3 primary and 3 secondary clearly label these aims primary and secondary.

7.3 **Please provide a summary of the present knowledge relevant to the research and make citation to any applicable scientific literature:**

This is your literature search and bibliography. Also known as

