In the NICU a work area has been identified which has a sink, storage area, and work surface. The work surface will be cleansed with a sterilization cloth, followed by handwashing and then retrieving the milk from the refrigerator using universal precautions. The 24 hour supply will be mixed into one clean mixing bottle large enough to accommodate the entire 24 hours supply. It will be homogenized by inverting the bottle 10 times. A 10 ml aliquot of the sample will be transferred into a container labeled with subject number and taken for analysis. The remainder of the milk will be repackaged into containers and labeled as one batch. The Miris human milk analyzer is a mid infrared that reports the amount of energy absorbed at each wavelength. The amount of fat (grams), lactose (grams), total protein (grams), true protein (grams), and energy (kcal) per 100 ml will be reported. The milk will be then fortified per protocol (control group), or with targeted fortification (intervention group) as described above.

In the NICU infants are weighed on a daily basis, as clinical condition allows; weekly head circumference, length, and either flank skin fold or mid upper arm circumference (dependent on weight). As standard of care infants <1500 g at birth have a PEAPOD measurement prior to discharge to evaluate body composition. The measurements will be performed by nursing staff on routine basis and will not be blinded to the group assignment, as the bedside nurse will also likely be assisting in preparing the feeds for the infant. The Peapod assessment is performed by CRU staff as standard of care for these patients prior to discharge, they will be blinded to the group assignment but the NICU staff (nursing, nurse practitioner, or fellow) accompanying the patient to the measurement will not be blinded.

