- Mothers collect a 24hr supply of breast milk once per week, from which a study team member will obtain a 10 ml representative sample for analysis. The 24hr collection of breast milk will be mixed into a clean container that can accommodate the entire volume. It will be homogenized and a 10 ml sample removed for

analysis. The remaining breast milk will be repackaged and placed back into the refrigerator in the NICU.

- After analysis, the milk for the following 1 week will be labeled and batched together
- For donor breast milk, each 'lot' will be analyzed and labeled for future use
- Analysis will take place at MetroHealth in the lab, using the Miris human milk analyzer. The amount of fat (grams), lactose (grams), total protein (grams), true protein (grams), and energy (kcal) per 100 ml will be reported and used for calculations.
- Infants will have birth measurements obtained, daily weight, weekly anthropometric measurements, and body composition measurement prior to discharge. The measurements will take a few minutes to obtain on routine basis per NICU protocol. The Peapod (body composition) measurement will take approximately 20 minutes total traveling from the NICU to CRU and back, but the actual assessment takes 2-3 minutes. This will be done with the infant is medically stable and approaching discharge.

The subjects will be in the study from time of consent to 4 weeks following the achievement of full enteral feedings, which may range from 6 weeks to 12 weeks depending on the birth weight and the clinical status of the infant. The smallest babies will take the longest to increase to full feeds due to the slow feeding protocol.

8.7 Please attach study design/subject visit schedule here:

Name	Description
There are no items to display	

If you have an electronic schedule of study visits and/or procedures please attach here.

View: 09-00 Inclusion/Exclusion Criteria

9.0 Inclusion/Exclusion Criteria:

9.1 What are the inclusion criteria? Put this information in bullet form:

Premature infants <1500 g
Mother consenting to provide breast milk or use of donor breast milk

Please list inclusion criteria.

9.2 What are exclusion criteria? Put this information in bullet form:

Infants with major congenital malformations
Infants with medical conditions precluding them from having breast milk
Mothers with medical conditions that preclude them from providing breast milk
Insufficient breast milk supply
Refusal of donor breast milk

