9.4 Will you exclude women and minorities, or persons under 21 from enrollment?

No

Check yes or no.

9.5 If yes, which groups are you excluding? Provide justification for your decision.

List groups to be excluded then provide justification.

9.6 Attach Documents:

Name	Description
There are no items to display	

If you are unable to fit your answers in the text boxes provided please attach as a word document.

View: 10-00 Risk/Benefits

10.0 Assessment of Risk I:

10.1 Identify and distinguish between those procedures that are standard versus those that are experimental. Include the frequency and duration of each activity and the total length of subject participation:

Standard procedures: Pumping and providing expressed breast milk, documentation of baby demographics, weekly anthropometric measurements, PEAPOD prior to discharge, Metrohealth standard feeding protocol.

Please distinguish between those procedures that are standard versus those that are experimental. Describe in detail all experimental procedures.

Experimental procedure: Weekly analysis of small aliquot of breast milk with Miris mid infrared human milk analyzer, targeted fortification of breast milk to achieve protein goal of 4g/kg/day and calories 100-130 kcal/kg/day, fortification of breast milk specifically for each mother/infant.

Deviation from standard Metrohealth NICU practice: collection of 24 hour supply of breast milk, analysis of breast milk content, targeted individualized addition of protein and fat. All other procedures are the standard of practice in NICU.

The measurements will take a few minutes to obtain on routine basis per NICU protocol. The Peapod (body composition) measurement will take approximately 20 minutes total traveling from the NICU to CRU and back, but the actual assessment takes 2-3 minutes. This will be done with the infant is medically stable and approaching discharge. Analysis of the breast milk will take approximately 20 minutes per sample, including the time to prepare the sample for analysis and analysis using the Miris human milk analyzer.

The subjects will be in the study from time of consent to 4 weeks following the achievement of full enteral feedings, which may range from 6 weeks to 12 weeks depending on the birth weight and the clinical status of the infant. The smallest babies will take the longest to increase to full feeds due to the slow feeding protocol.

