10.2 Describe any therapeutic alternatives to the research that may exist. How are they different from those procedures that subjects would normally undergo?

Therapeutic alternative is standard fortification of breast milk per protocol. This uses reported average protein and caloric content of breast milk and adds standard amounts of fortifier. Content of breast milk is variable between mothers and has wide range. They also have the option to not participate in the study and receive standard NICU management.

Describe any therapeutic alternatives. Can subjects receive this drug or device outside of a research study?

10.3 What are the outcome variables and how will they be analyzed? What are the statistical and analytical methods that will be used? Note this section can be copied from the NIH Grant Application or from the Statistical and Analytical Methods section of the industry trial protocol.

The outcome variables are the anthropometric measurements including daily weight; weekly length, head circumference, skin fold thickness or mid upper arm circumference; and PEAPOD body composition measurements prior to discharge.

Define outcomes and describe data analysis, please include a power calculation.

Our primary outcome is body composition, as measured by air displacement plethysmography (PEAPod). As standardized assessment of body composition is relatively new in the preterm infant population, we are using clinical judgment to determine that a difference in fat free mass z-score (from data from Norris T, 2019) of 0.5 is clinically significant. To detect a difference at alpha $\alpha=0.05$ with 80% power, 25 infants per group are required. This is a realistic goal for clinical enrollment, due to the historical MetroHealth NICU census composition. According to the census at MetroHealth, the total number of infants with birth weight less than 1500 g for 2016 was 81 infants, and in 2017 was 84 infants.

If the requested information does not fit in the text box please attach a word document.

10.4 If the above requested information does not fit in the text box please attach a word document here:

Name	Description
There are no items to display	

View: 10-01 Risk/Benefits

10.1 Assessment of Risk II:

10.5 List and quantitate the risks involved for each experimental procedure in bullet form. Identify risks as common (greater than 10%) uncommon (greater than 1% up to and including 10 %) rare (1% or less). This must match the risks listed in the Consent Form:

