Targeted fortification- rare, some babies may have elevated BUN which is routinely monitored in the NICU, or rare, feeding intolerance

Select all that apply.

There is also risk of breach of confidentiality, but this is rare. Data will be stored securely, only key study investigators will have access to data, and it will be deidentified and only the PI will have access to the key.

The probability and magnitude of harm or discomfort anticipated in the

research are no greater than those ordinarily encountered daily during routine care while admitted to NICU.

10.6

Are there defined stopping rules? Yes No

Describe in enough detail for the IRB to assess safety.

What are the stopping rules for the study? What are the conditions under which a subject will be withdrawn from the study for safety reasons, i.e. disease progression?

Intolerance to fortification, excessive emesis or recurrent, otherwise unexplained, abdominal distention.

What findings, events, or conditions would require a research subject to be removed from the study? (i.e. disease progression)

Clinical worsening, acute decompensation of infant precluding them from receiving enteral feeds.

If a patient become acutely ill and significantly decompensates they may be removed from the study. Ex: sepsis, abdominal distention, blood in the stool, respiratory failure with increasing need for respiratory support. If a patient becomes comfort-care only and no longer receiving enteral feeds they may also be removed from the study.

10.7

What Category of risk will study participants be exposed too?

Name

[Privacy](#)

[Other](#)

Should be consistent with risks listed in the Consent Form.

10.8

If Other listed above please specify:

Infants will need to leave the NICU for PEAPOD body composition measurement. This will be done once they are determined to be medically stable and ready for discharge.

A text box is provided for further explanation.

A text box is provided for further explanation.

10.9

Describe the availability of medical or psychological services that participants might require as a consequence of participation in this the research:

The participants will have medical services available in the NICU at their disposal during the entirety of involvement in the study. Every effort will be made to obtain resources to support mother's pumping activities and providing of breast milk- pumping room with breast pumps and supplies, lactation services, nutrition services.

10.10

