Definitions: Data are considered to be existing data only if they were in place or "on the shelf" prior to the submission of the research protocol to the IRB. Data are considered prospective if they are created and collected as part of the research i.e. from surveys, questionnaires.

Tell the IRB why you are collecting this data i.e. to verify inclusion criteria.

B. Why are you collecting this data?

What will be the purpose of collecting and/or reviewing the data (new data or existing data).

After intervention of targeted fortification vs standard fortification anthropometric measurements and body composition will be measured. Daily weight; weekly length, head circumference, skinfold thickness or mid upper arm circumference; and PEAPOD body composition prior to discharge. These will be measured to evaluate growth parameters of infants receiving individualized targeted fortification to meet nutritional goals vs standard fortification.

14.2

If you are collecting existing data:

Specify the types of existing data you will use in this study.

Specify the type(s) of existing data sources you will use (medical records, school records, publicly available records, existing database). If you are collecting data from an existing database and that database contains PHI, you must provide the IRB Approval letter (attach to Section 27.00 Additional Documents).

We will use medical records for mother and baby to obtain demographics.

Time frame i.e. last 10 years or from 1990-2000.

What is the timeframe of the existing data you wish to review? (i.e. 2000-2006)

Any time before study enrollment.

14.3

If you are collecting prospective data:

Where or how will the data be obtained? (i.e. surveys, questionnaires, psychological tests)

Where will data be obtained? i.e. survey.

NICU admission log and electronic medical records. Milk samples will be analyzed in the lab at MHMC using the Miris human milk analyzer. PEAPOD body composition measurements will be done at the CRU.

14.4

How will the data you collect be identified?

Types of Data Identification:

Name

Deidentified/Confidential- Data will be linked to subject(s) via a code or indirect identifier (i.e. study IDs or numbers)

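### Section 7.2 can place the primary outcome at 4 weeks after full feeds, but the one planned PEAPOD is triggered by nearness to discharge, so infants not near discharge then have no planned measurement at that time

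*Combined protocol and SAP*

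**What the plan says.** Section 7.2 (specific aims) sets the primary outcome as "body composition measurement 4 weeks after achieving full feeds with targeted fortification, or at NICU discharge, whichever comes first".

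The sections that say when the PEAPOD is done fall into two groups.

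- Trigger wording. Section 8.6, and the same sentence again in 10.1: "This will be done with the infant is medically stable and approaching discharge". Section 10.8: "This will be done once they are determined to be medically stable and ready for discharge".
- Neutral wording. The CRU nursing visits table (3.01), which lists one visit: "CRU will obtain PEAPOD prior to discharge". Section 8.4: "As standard of care infants <1500 g at birth have a PEAPOD measurement prior to discharge to evaluate body composition". Section 10.3: "PEAPOD body composition measurements prior to discharge". Section 14.1: "PEAPOD body composition prior to discharge". Section 10.1 also lists the test among the standard procedures.

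Sections 8.6 and 10.1 end participation 4 weeks after full enteral feeds, put at 6 to 12 weeks from consent. Sections 8.4 and 8.6 specify fortification for 4 weeks after full feeds. Two entries bear on length of stay: CRU item 1.06 gives about 90 inpatient days per subject, and item 6 of the supplemental form for research with children puts discharge at about 3 to 4 months of age.

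**The concern.** Section 7.2 has two limbs, and the earlier one applies. The discharge limb has a test attached to it. The 4-week limb has none: no section schedules a PEAPOD at that time, only one is planned, and the condition for doing it is nearness to discharge. If an infant reaches 4 weeks after full feeds while still some way from discharge, following the plan produces no value at the time that defines its primary outcome. The value it does get comes after stated participation has ended, and after the specified fortification period.

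Two things are left open for the primary endpoint. One is whether a PEAPOD taken later than the 7.2 time counts as the primary outcome or as missing. The other is whether the trial estimates the effect at the end of the specified fortification period or at a variable time after it. If these are settled once results are visible, the choice of endpoint can depend on the data.

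**Working it through.** **1. Which statements conflict.** A test before discharge can still be a test at 4 weeks, so the neutral wording in CRU 3.01, 8.4, 10.3 and 14.1 fits either reading. The conflict lies between 7.2 and the trigger wording in 8.6, 10.1 and 10.8. Because 8.6 and 10.1 share one sentence, that is two distinct statements against 7.2.

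**2. When the 4-week point falls.** The plan's own figure is 6 to 12 weeks from consent (42 to 84 days). It can be compared with the feeding schedule in 8.4.

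Assumptions: 12 feeds a day (the interval for 1251-1500 g is not stated), no interruptions, birth weight as the ml/kg base, 500 g as the lower limit of the lightest stratum, and ±1 day for rounding.

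For the three lighter strata, day of full feeds = NPO days + priming days + days to 100 ml/kg/day + 5 days to 150 ml/kg/day. The heaviest stratum advances by 20 ml/kg/day directly to 150. The 4-week point is 28 days later.

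| Birth weight | Full feeds (day) | +28 (day) |
|---|---|---|
| <750 g | 10 + 10 + (8 to 12 steps × 2) + 5 = 41-49 | 69-77 |
| 750-1000 g | 7 + 7 + (11 to 15 steps × 1) + 5 = 30-34 | 58-62 |
| 1001-1250 g | 4 + 4 + (7 to 9 steps × 2) + 5 = 27-31 | 55-59 |
| 1251-1500 g | 1 + 2 + 7 = 10 | 38 |

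Step counts, for example at 500 g: priming gives 0.5 × 12 = 6 ml/day, each step adds 6 ml/day, and the target is 50 ml/day. (50 − 6)/6 = 7.3, so 8 steps.

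Overall the 4-week point is at day 38 to 77, or 5.4 to 11.0 weeks, broadly in line with the stated 6 to 12 weeks. If weight during advancement is 50% above birth weight, the ranges from lightest to heaviest stratum become 77-89, 64-70, 65-71 and 38.

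**3. Distance to discharge.** Taking 90 inpatient days as age at discharge:

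- from the feeding steps: 90 − 77 = 13 to 90 − 38 = 52 days;
- from the 6 to 12 weeks, with consent near birth: 90 − 84 = 6 to 90 − 42 = 48 days;
- with the heavier weights, the short end is 90 − 89 = 1 day.

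The 3-to-4-month figure (about 91 to 122 days) also lies beyond 84 days. Both stay figures are approximate and pooled over birth weights, whereas the 4-week point differs by stratum. The gaps show the order of magnitude and are not a distribution.

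**The case against.** The best defence is that nearness to discharge has no stated window. A stable infant who has been on full feeds for 4 weeks could be regarded as approaching discharge, and at the upper end of 8.6 (84 days against a 90-day stay) the two times nearly coincide. That reading can rescue some infants under 8.6 and 10.1. It does not fit 10.8, which requires readiness for discharge, and it does not help an infant several weeks from going home.

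Infants discharged before 4 weeks after full feeds are on definition under 7.2. That stands, and they should not be counted as off-time.

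A reader might infer that variable test timing biases the comparison. The documents do not support that. The same trigger applies in both arms, allocation is stratified by birth weight, and the CRU staff who perform the PEAPOD are blinded. Caregivers are not blinded, so timing could differ by arm, but nothing shows that it would, or in which direction.

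It may also be said that the z-score in 10.3 deals with age at test. The plan names only a cited dataset and does not say how the score is standardised. A z-score would in any case not settle whether the effect is estimated at 4 weeks or later.

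**Conclusion.** The point holds as a contradiction in the text about when the primary outcome is measured. It is wrong as written, because following the plan leaves infants who are still in the NICU and not near discharge at 4 weeks without a value at the defined time. On the plan's figures the 4-week limb would often come first, with gaps of roughly 13 to 52 days (feeding steps) or 6 to 48 days (8.6 range). These rest on a 90-day stay in every stratum, uninterrupted feeding advances and consent near birth.

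Three stronger readings go too far. One is that every PEAPOD statement contradicts 7.2: those that only place the test before discharge do not. Another is that most of the 60 planned mother/baby couples lack a valid primary outcome: no distribution of discharge times is given, so the share cannot be computed. The third is that there are competing values to choose between: only one PEAPOD per infant is planned. Confidence is high for the conflict itself; the size and direction of any effect on the result are unknown.

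**What to change.** Before any data are seen, state one primary time point and make 7.2, 8.6, 10.1, 10.3 and 10.8 agree with it. The choice between the two options is the sponsor's.

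**Option A.** Restate 7.2 as the fat-free mass z-score named in 10.3, taken at the single standard-of-care PEAPOD before discharge. Extend stated participation in 8.6 and 10.1 to that test, and record its date. For infants still in the NICU at 4 weeks after full feeds, report by arm the days from that point to the test (negative if the test came first). Count infants discharged earlier as on time, and list separately those who never reach full feeds. The cost is wording and one recorded date, with no extra test. Any statement of duration in the consent form would have to match; those pages were not available here. The downside is a variable interval between the end of the fortification period and the measurement.

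**Option B.** Keep 7.2 and reconcile the trigger wording in 8.6, 10.1 and 10.8 with it, stating how infants who cannot be transferred at 4 weeks are handled in the analysis. This keeps the endpoint at the end of the fortification period but is less clearly cheap. It separates the test from the discharge-readiness condition in 10.8, may leave some infants without a value, and any PEAPOD beyond the one listed as standard in 10.1 would need its own risk statement.
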